|-------------|------------------|------------------------------------------------------------------------------------------------------------------------------------------------------------------------------------------------------------------------------------------------------------------------------------------------------------------------------------------------------------------------------------------------------------------------------------------------------------------------------------------------------------------------------------------------------------------------------------------------------------------------------------------------------------------------------------------------------------------------------------------------------------------------------------------------------------------------------------------------------------------------------------------------------------------------------------------------------------------------------------|
| Version 1.0 | July 30, 2021 | Initial draft |
| Version 2.0 | December 9, 2021 | Following changes were made: 1. The Medline clinical designee or Medline Director of Clinical Operations name was changed from [name] to [name]. 2. The Medline clinical designee or Medline Director of Clinical Operations phone number was also updated. |
| Version 3.0 | May 9, 2022 | Following changes were made: Medline Industries, Inc. was changed to Medline Industries, LP throughout the document. Section 1.1: i) An addition was made in the study population section to indicate that the same blood draw value can be used for multiple sensors placed simultaneously. ii) The description of the site was changed from multiple centers to multiple neonatal intensive care centers in order to be more specific. The study staff was changed to PI or designee throughout the document where applicable. Section 1.2: An addition was made in the required assessments and activities column to indicate that the pulse oximeter data will be collected to determine SpO₂ from same or different hands and/or feet using one or both of the provided sensor types. Section 4.1: Since the data were collected from a convenience sample of subjects, randomization |

Accuracy of SpO₂ of reprocessed pulse oximetry sensors compared to SaO₂ assessed by CO-oximetry in neonates MED-2020-DIV65-001 May 9, 2022 V 3.0

MEDLINE

1. PROTOCOL SUMMARY

1.1. Synopsis

| Title: | Accuracy and precision of peripheral capillary oxygen saturation of |
|--------|---------------------------------------------------------------------|
| | reprocessed pulse oximetry sensors compared to oxygen saturation |
| | in arterial blood samples assessed by CO-oximetry in neonates. |

- **Study Description:** Pulse oximetry helps in measuring peripheral capillary oxygen saturation (SpO₂) continuously and non-invasively, and provides an indirect measurement of arterial oxygenation (SaO₂) based on the red and infrared light-absorption characteristics of oxygenated and deoxygenated hemoglobin. Uses of pulse oximetry include detection of hypoxia, avoidance of hyperoxia, titration of fractional inspired oxygen, and enabling weaning from mechanical ventilation. Arterial blood gas (ABG) analysis, such as by the use of CO-oximeter, provides a direct measurement of SaO₂. However, ABG analysis requires time, expense, and arterial access. Therefore, this study aims to validate the SpO₂ accuracy of pulse oximetry sensors (manufactured by Nellcor and Masimo, and reprocessed by Medline Industries, LP) in neonates as compared to ABG measurements as part of their clinical standard of care (SOC), as assessed by CO-oximetry.
- **Objective:**To validate the SpO_2 accuracy, bias, and precision of Medline's
reprocessed pulse oximetry sensors as compared to SaO_2 in arterial
blood samples as assessed by CO-oximetry in neonates.
- **Endpoint:** Pulse oximeter and co-oximeter reading pair used to determine the accuracy of each pulse oximeter by evaluating accuracy root mean square (A_{RMS}), bias, and precision.

MEDLINE

| Study Population: | A total of at least 80 total data pairs per sensor will be collected. These should be collected from a minimum of 27 subjects such that there are no more than three pairs per subject (maximum of 3 blood draws). The same blood draw value can be used for multiple sensors placed simultaneously. |
|-----------------------------------------------------------|------------------------------------------------------------------------------------------------------------------------------------------------------------------------------------------------------------------------------------------------------------------------------------------------------------------------------------------------------------------------------------------------------------------------------------------------------------------------------------------------------------------------------------------------------------------------------------------------------------------------------------------------------------------------------|
| | Inclusion Criteria Subjects who are postnatal 28 days or younger (neonates) Subjects who are likely to receive one or more ABG measurements as part of their clinical SOC. Subjects who weigh less than 5 Kg (weight range for the sensors) |
| | Exclusion Criteria Subjects with current signs and symptoms of a clinically significant Patent Ductus Arteriosus (PDA) combined with a current or planned arterial line placement which will affect the validity of the co-oximetry measurement Subjects with physical malformation of hands, fingers, feet, or toes that would limit the ability to place sensors for this study Subjects judged by the Principal Investigator (PI) to be inappropriate for participation in this study Subjects for whom placing a pulse oximeter will cause dermatological issues (e.g. allergic to foam rubber or adhesive tape) |
| Phase: | Post-Market |
| Description of Sites/Facilities Enrolling subjects: | Multiple neonatal intensive care centers |
| Description of Study: | Data collection will take place at the sites. The PI or designee will place one or both of the pulse oximeter sensors (Medline ReNewal [™] Reprocessed Masimo LNCS Series SpO2 Adhesive Sensors, Neo (2329) and Medline Renewal [™] Reprocessed Nellcor [™] OxiMax SpO2 Sensor, MAXN) on hands and/or feet of the subjects according to the IFU and record the readings. The arterial blood sample used in this study will be taken in the normal course of care and will be measured in the reference CO-oximeter |

Accuracy of SpO₂ of reprocessed pulse oximetry sensors compared to SaO₂ assessed by CO-oximetry in neonates MED-2020-DIV65-001 May 9, 2022 V 3.0

for SaO₂. This arterial sample will be obtained from a systemic artery.

Anticipated Six months to one year **Enrollment period:**

Subject Duration: Approximately 15 episodic minutes at the time of the blood draw (the sensor, disconnected from the monitor, may stay on the subject for the maximum allowable duration of sensor use) or per the facility SOC.

1.2 Schedule of activities

| REQUIRED ASSESSMENTS & ACTIVITIES | Screening Visit Day 0 ^a | Study Visit Day 1 ^a |
|---------------------------------------------------------------------------------------------------------------------------------------------------|---------------------------------------|-----------------------------------|
| Informed consent and screening form ^b | X | 2007 1 |
| Arterial blood sample, which is collected in the normal course of care, will be measured in the reference CO-oximeter for SaO ₂ | | Х |
| Pulse oximeter data will be collected to determine SpO ₂ from same or different hands and/or feet using one or both of the provided | | Х |
| sensor types | | |
| Adverse event assessment | X | X |
| a: Day 0 and Day 1 visits can be on the same day. b: Informed consent and screening may be performed on different day | VS. | |

2. INTRODUCTION

2.1. Background & Rationale

Pulse oximetry helps in measuring SpO₂ continuously and non-invasively, and also provides an indirect measurement of SaO₂ based on the red and infrared light-absorption characteristics of oxygenated and deoxygenated hemoglobin. The ABG analysis, such as by the use of CO-oximeter, provides a direct measurement of SaO₂.^{1,2} However, ABG analysis requires time, expense, and arterial puncture; therefore non-invasive techniques that give similar results are being investigated.

This study aims to validate the SpO₂ accuracy and precision of pulse oximetry sensors (manufactured by Nellcor and Masimo, and reprocessed by Medline Industries, LP) in neonates as compared to ABG measurements as part of their clinical SOC, as assessed by CO-oximetry.

2.2. Study Products

2.2.1. Medline ReNewal[™] Reprocessed Masimo LNCS Series SpO2 Adhesive Sensors, Neo (2329) (henceforth referred to as "Masimo sensor")

The Masimo sensors are indicated for monitoring SpO_2 and pulse rate for use with neonatal patients in hospitals, hospital-type facilities, mobile, and home environments. Further information on these sensors can be found in Appendix 11.1.1.

2.2.2. Medline RenewalTM Reprocessed NellcorTM OxiMax SpO2 Sensor, MAXN (henceforth referred to as "Nellcor sensor")

The Nellcor sensors are used for monitoring SpO_2 and pulse rate on neonates. Further information on the products can be found in Appendix 11.1.2.

2.3. Risk/Benefit Profile

2.3.1. Potential Study Risks

Masimo and Nellcor sensors are contraindicated for use on patients who exhibit allergic reactions to foam rubber products and/or adhesive tape. While we are screening to not include subjects with dermatological issues, some subjects with unidentified issues may be enrolled. Subjects will be under the care of a physician who will be able to appropriately address any potential reaction from these products. Although protective measures are taken by the sponsor and site, there is a risk of potential disclosure of Protected Health Information (PHI) by being enrolled in this study.

Accuracy of SpO₂ of reprocessed pulse oximetry sensors compared to SaO₂ assessed by CO-oximetry in neonates MED-2020-DIV65-001 May 9, 2022 V 3.0 MEDLINE

2.3.2. Potential Study Benefits

There are no direct benefits to the neonates enrolled in this study or to their families. The societal benefit is knowing if the reprocessed sensors are accurate and precise.

2.3.3. Assessment of Potential Risk/Benefit Profile

The use of these products presents minimal risk for subjects enrolled in this study, while offering the potential for societal benefit. Therefore, the risk-benefit profile for the study is favorable.

3. OBJECTIVES AND ENDPOINTS

| OBJECTIVE | ENDPOINT | JUSTIFICATION FOR ENDPOINT |
|------------------------------------------------------------------------------------------------------------------------------------------------------------------------------------------------------------------------------------|--------------------------------------------------------------------------------------------------------------------------------------------------------------------------------------------------------|-----------------------------------------------------------------------------------------------------------------------------------|
| To validate the SpO ₂ accuracy, bias, and precision of Medline's reprocessed pulse oximetry sensors as compared to SaO ₂ in arterial blood samples as assessed by CO-oximetry in neonates. | Pulse oximeter and co- oximeter reading pair used to determine the accuracy of each pulse oximeter by evaluating accuracy root mean square (A _{RMS}), bias, and precision. | CO-oximetry is an invasive technique requiring blood draw(s), whereas pulse oximetry does not involve any blood draw. |

4. STUDY DESIGN

4.1. Overall Design

This study is a multi-site, open-label clinical trial validating the SpO₂ accuracy and precision of Medline's reprocessed pulse oximetry sensors as compared to SaO₂ in arterial blood samples as assessed by CO-oximetry in neonates. The data collection will take place at the sites. The PI or designee will place the Masimo and Nellcor sensors on hands and/or feet of the subject according to the IFU and record the reading. The arterial blood sample used in this study will be taken in the normal course of care and will be measured in the reference CO-oximeter for SaO₂. This arterial sample will be obtained from a systemic artery.

4.2. End of Study Definition

A subject's participation in the study may end at several critical points:

• When the maximum number of blood draws, as per SOC (three), has been reached

- The maximum duration of sensor wear time has been reached, as per SOC or IFU, whichever occurs first.
- The PI or patient care team believes it is in the subject's best interest to discontinue in the study.
- Parent or legal guardian of the subject withdraws the subject from the study for any reason.

If the subject withdraws from the study, they will be replaced by another subject.

The study will be considered complete upon issuance of a Clinical Study Report that has been approved by the Clinical Affairs Director.

5. STUDY POPULATION

5.1. Inclusion Criteria

Subjects, who satisfy *ALL* of the inclusion criteria below, will be eligible to participate in the study:

- Subjects who are postnatal 28 days or younger (neonates).
- Subjects who are likely to receive one or more arterial blood gas measurements as part of their clinical standard of care
- Subjects who weigh less than 5 Kg (weight range for the sensors).

5.2. Exclusion Criteria

Subjects, who meet *ANY* of the criteria below, will be ineligible for the study:

- Subjects with current signs and symptoms of a clinically significant PDA, combined with a current or planned arterial line placement which will affect the validity of the co-oximetry measurement.
- Subjects with physical malformation of hands, fingers, feet, or toes that would limit the ability to place sensors for this study.
- Subjects judged by the PI to be inappropriate for participation in this study.
- Subjects for whom placing a pulse oximeter will cause dermatological issues (e.g., allergic to foam rubber or adhesive tape).

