6.1.2 Eligibility Screening

Potential subjects will be screened for eligibility by the site PI, via a combination of the screening form provided by Medline Industries, LP, and by a review of the potential subject's medical chart by the site PI and/or their staff.

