6.2. Day 1 – Study visit

6.2.1. Collection of arterial blood sample and measurement by CO-oximeter

The arterial blood sample will be collected in the normal course of care and will be measured in the reference CO-oximeter for SaO_2 . The time of the arterial blood sample will be recorded on the CRF by the PI or designee or patient's care team using a calibrated clock as the reference time. No more than three blood draws, resulting in three data pairs per sensor in a subject, will be used for this study. Data pairs may be concurrently collected for each of the two sensors type if sensors can be placed on separate extremities.

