6.2.6 Moving and Removing Sensors

The sensors may remain on the subject up-to the same duration as would be used for a SOC pulse oximeter. Thus, the duration the sensors remains on the subject is variable but limited by the SOC for each subject.

Subject specific sensors that are removed in between samplings will be secured by the study team until the next time point use. Sensors may be reused on the same subject but will not be used on another subject. Once a subject has completed participation, their sensor will be collected and returned to Medline Industries, LP.

The study or clinical team may move a sensor from location to location on the subject's body to facilitate care and measurement quality.

If the subject has multiple arterial blood samples collected, 6.2.1-6.2.6 can be repeated up to three times using the same sensor. If a new sensor is used, it shall be noted in the CRF.

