8.3. Populations for Analysis

All data pairs will be included for analysis, unless at the time of data acquisition any one or more of the following is true: (1) the SpO2 value is >100%; OR (2) the SpO2 value is \leq 0%; OR (3) the heart rate measurement derived from the pulse oximeter is 0 beats per minute; OR (4) the research personnel collecting the data notes an anomaly in the measurement on the CRF at the time of data collection before data analysis begins. Any such designated outliers and/or anomalous data will be explained and any data that is excluded from the analysis will be justified in the final report.

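### The PDA/arterial-line exclusion protects the CO-oximetry reference but is assessed only at screening; later pairs taken while it is met stay in by default and cannot be identified

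*Combined protocol and SAP*

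**What the plan says.** Section 5.2 excludes infants showing "current signs and symptoms of a clinically significant PDA, combined with a current or planned arterial line placement which will affect the validity"; the validity in question is that of the CO-oximetry reading. Three elements are joined: a clinically significant PDA now, an arterial line in place or planned, and an effect on the reference.

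Eligibility is a Day 0 step. Under 6.1.2, "Potential subjects will be screened for eligibility by the site PI", using the screening form and the medical chart. In the schedule (1.2) the row "Informed consent and screening form" is marked for Day 0. The legible Day 1 activities are the blood sample, the SpO2 reading and the adverse event assessment. A footnote adds that "Day 0 and Day 1 visits can be on the same day"; no maximum interval is stated.

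On repeat sampling, 6.2.1 says "No more than three blood draws, resulting in three data pairs per sensor in a subject, will be used for this study". Section 6.2.6 says that steps 6.2.1 to 6.2.6 "can be repeated up to three times using the same sensor". The eligibility step, 6.1.2, lies outside that range.

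On the analysis set, 8.3 says "All data pairs will be included for analysis, unless at the time of data acquisition any one or more of the following is true". The four conditions are SpO2 above 100%, SpO2 at or below 0%, an oximeter heart rate of zero, and an anomaly in the measurement noted by staff on the CRF at collection.

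**The concern.** Most eligibility criteria describe who the infant is. This one describes whether the reference can be trusted, and its wording is in the present tense. An infant can pass it correctly at Day 0 and meet it at a later draw, because a PDA becomes clinically significant or because a line that was not foreseen at screening is placed. The plan has judged that combination serious enough to keep an infant out, but it does not apply the judgement when the pairs are collected.

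Any resulting SpO2–SaO2 difference would be charged to the sensor. A_RMS squares each difference, so a few large ones weigh more than their number suggests. A_RMS is also the only accuracy measure in 8.4 with a stated expectation (at most 3%).

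The problem could not be repaired afterwards. The CRF items in 6.2.1, 6.2.2 and 6.2.7 include neither PDA status nor the arterial sampling site, so an analyst could not find the affected pairs or run a sensitivity analysis without them.

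**Working it through.** **The plan's own figures.** Section 8.1 doubles 40 pairs to 2 × 40 = 80 per sensor. At no more than three pairs per infant, 80/3 = 26.7, which rounds up to 27 subjects. Both reproduce, and neither is disputed here.

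**How many pairs come from repeat draws.** With the minimum 27 infants, at most 27 of a sensor's 80 pairs are first pairs, so 80 − 27 = 53 (66%) come from second or third draws. More infants would lower this share.

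**How long the window can be.** Section 4.2 lets participation run to the maximum wear time under SOC or the IFU, whichever comes first. The Masimo IFU gives up to 168 hours of monitoring time. The window can therefore be days, though it can also be a single day.

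**Routes by which an affected pair could leave the data**
- Section 4.2: the investigator or care team may end participation, but on the ground of the subject's best interest, not the validity of the reference.
- Section 5.2, investigator judgement: this too is an eligibility criterion, with no stated re-application.
- Section 8.3, conditions 1 to 3: these test only the oximeter's SpO2 and heart rate. A plausible reading on an affected infant passes all three.
- Section 8.3, condition 4: available at staff discretion, without mention of PDA, arterial line or loss of eligibility.

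**Illustration of size.** Inputs from the documents: n = 80 pairs per sensor (8.1), and adult A_RMS over 70–100% of s = 1.7 for MAXN and 1.6 for Neo 2329 (IFU tables). Assumptions not in the documents: k pairs carry an added error of d points, independent of the sensor's own error, with d from 5 to 10. Then

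A_RMS = √(s² + (k/80)·d²).

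For s = 1.7, k = 3, d = 8: √(2.89 + 0.0375 × 64) = √5.29 = 2.30.

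| s = 1.7 | d = 5 | d = 8 | d = 10 | d at which A_RMS = 3% |
|---|---|---|---|---|
| k = 3 (one infant, all draws) | 1.96 | 2.30 | 2.58 | 12.8 |
| k = 6 (two infants, all draws) | 2.18 | 2.77 | 3.22 | 9.0 |

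The last column is √((9 − s²)·80/k). With s = 1.6 it becomes 13.1 and 9.3. With an assumed neonatal s of 2.5 it becomes 8.6 and 6.1.

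**Bias.** If the added errors share a sign, mean bias moves by k·d/80. For k = 3 that is 0.19 points at d = 5 and 0.38 at d = 10.

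**Sensitivity to independence.** If the sensor's own mean error in the affected pairs is b, the term 2(k/80)·d·b is added under the root. For s = 1.7, k = 3, d = 8 and an assumed b of −1 or +1, that term is −0.6 or +0.6, and A_RMS is √4.69 = 2.17 or √5.89 = 2.43 instead of 2.30.

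**The case against.** Four points on the other side are fair, and each limits what can be claimed.

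- A reader might infer that the protocol calls any pair from an infant with a later significant PDA invalid. It does not. Invalidity is tied to PDA together with an arterial line that affects the measurement, and a line already planned at screening falls within the wording. The gap is confined to the full criterion arising after Day 0.
- A reader might infer that 8.3 forces affected pairs to be kept. Condition 4 can be read to reach a disturbed reference, because 8.1 defines a pair as a sensor reading with a blood gas reading, and 5.2 itself speaks of the co-oximetry measurement. Sections 8.3 and 8.4 also require outliers to be explained and exclusions justified. But nothing prompts staff to look for this condition, and its use may differ between sites. It narrows the gap without closing it.
- The footnote "Informed consent and screening may be performed on different day" might be taken to place screening and the study visit on different days. Its natural reading separates consent from screening. The other footnote allows Day 0 and Day 1 to coincide, so the gap to the first draw may be zero. It is simply not bounded, and later draws can still follow.
- The size rests on an assumed shift, and a PDA arising after screening need not affect all of an infant's draws. Under the independence assumption the added error can only raise A_RMS, so it would work against the sensor and would not create a false success.

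**Conclusion.** The concern holds in limited form. The PDA/arterial-line criterion protects the reference at the draw, but it is assessed only at Day 0. Pairs collected after the full criterion arises are included by default, and the listed CRF fields cannot identify them.

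The likely effect cannot be estimated, because the documents give neither how often this would happen nor how large the error would be. A reader might conclude that a few such pairs would decide the comparison with 3%. The documents' own figures do not support that: from the adult values of 1.6–1.7%, one infant's three pairs need a shift of about 13 points to reach 3%, and two infants' six pairs about 9. Crossing 3% takes a large shift, several infants, or a neonatal baseline already near the limit. Section 8.4 also words 3% as an expectation. Smaller shifts still move A_RMS noticeably, for example from 1.7% to 2.30% with three pairs at 8 points. These figures assume 80 pairs and independent added error. The change is worth making because it is cheap and because the information cannot be recovered from the planned CRF later.

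**What to change.** Change data collection and analysis only; blood draws remain part of standard care.

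- **6.2.1:** at each draw, and before the SaO2 result is seen, the investigator or designee records on the CRF whether the 5.2 PDA/arterial-line criterion is met (yes/no), together with the arterial sampling site. The pair is still collected.
- **8.3:** add a fifth, pre-specified condition that excludes flagged pairs from the primary A_RMS, bias and precision. Report the number of flagged pairs and the same three statistics with them included.

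The cost is one short CRF entry per draw and a sentence or two in each section. The entry needs the same judgement of clinical significance as screening does, so some variation between investigators will remain; recording it before SaO2 is known keeps that judgement independent of the reference result. A few pairs may need replacing to keep 80: three flagged pairs leave 77 and need at least one further infant, and six leave 74 and need at least two.

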6.2.2. Data collection using pulse oximeter

At or near the time the first blood sample is collected, the PI or designee will place one or both sensors (Masimo and/or Nellcor sensors) on the subject. If the subject is currently receiving biliruben light therapy, then the biliruben light must be turned off when the pulse oximeter sensor reading is taken. The PI or designee will record the SpO₂ measurement, the subject's heart rate, and the time and location of the measurement on the CRF using a calibrated clock as the reference time.

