11. APPENDIX

11.1 Study Products

11.1.1 Medline ReNewalTM Reprocessed Masimo LNCS Series SpO2 Adhesive Sensors, Neo (2329)

This Masimo sensor is indicated for monitoring SpO_2 and pulse rate for use with neonatal patients during no-motion conditions, and for patients who are well perfused in hospitals, hospital-type facilities, mobile, and home environments. This sensor is manufactured by Masimo and reprocessed by Medline Industries, Inc. The preferred site for use of this sensor is the foot, but across the palm and back of the hand can also be used. Sensor placement will be chosen at the discretion of the PI.

Accuracy of SpO₂ of reprocessed pulse oximetry sensors compared to SaO₂ assessed by CO-oximetry in neonates MED-2020-DIV65-001 May 9, 2022 V 3.0

Figure 11.1.1: Medline ReNewal[™] Reprocessed Masimo LNCS Series SpO2 Adhesive Sensors, Neo (2329)

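### The PDA exclusion depends on an arterial line, so an infant with a significant PDA sampled by puncture is not excluded by the named criterion, and any sampling-site difference counts as sensor error

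*Combined protocol and SAP*

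**What the plan says.** The exclusion in Section 5.2 has two parts joined together: the infant must currently show a clinically significant PDA, and this must be "combined with a current or planned arterial line placement which will affect the validity of the co-oximetry measurement". The synopsis (1.1) has the same rule.

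Nothing else in the plan requires a line. The inclusion criterion is "Subjects who are likely to receive one or more arterial blood gas measurements as part of their clinical standard of care" (5.1). On the source of the reference, Section 4.1 says only "This arterial sample will be obtained from a systemic artery". The background (2.1) notes that "ABG analysis requires time, expense, and arterial puncture".

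Sensors go "on hands and/or feet of the subject according to the IFU and record the reading" (4.1). For the Masimo sensor, "The preferred site for use of this sensor is the foot" (11.1.1), and 11.1.2 gives the same preference for the Nellcor sensor. For the SpO2 reading, the CRF takes "the time and location of the measurement on the CRF using a calibrated clock as the reference time" (6.2.2). For the arterial sample, Section 6.2.1 asks only for the time.

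**The concern.** The criterion states its own purpose, which is to keep out infants whose arterial sample would not be a valid reference. It does so through the sampling device. An infant with a significant PDA and no current or planned line meets only one of the two conditions, so the rule does not apply, although the blood gas may still come from an artery whose saturation differs from that under the sensor.

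At stake is the meaning of A_RMS, bias and the limits of agreement (8.4). All three treat SpO2 minus SaO2 as sensor error, so a true difference between sites would be charged to the sensor. One infant can supply three pairs per sensor, and A_RMS squares each difference. The artery is not among the items recorded, so affected pairs could not be picked out afterwards.

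**Working it through.** **The eligibility logic**

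| Infant with a significant PDA | Named PDA exclusion (5.2) | Inclusion on arterial gas (5.1) |
|---|---|---|
| Line current or planned, validity affected | Applies: excluded | Met |
| No line, routine gas by puncture | Does not apply | Met |

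**What else could catch the second row**

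- Investigator discretion (5.2): general, optional, no mention of PDA.
- Section 8.3: drops a pair for an SpO2 above 100% or at or below 0%, a heart rate of 0, or an anomaly noted at collection. PDA is not named, and a correct reading at another site need not look anomalous.
- Sections 6.2.4 and 6.2.5: these recognise that saturation or perfusion may differ between locations, but they match the two sensors to each other, not to the artery.

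**Inputs for the size**

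- 80 pairs per sensor, at most 3 per subject, minimum 27 subjects (8.1). Check: 80/3 = 26.7, rounded up to 27, which agrees with the plan.
- Adult A_RMS over 70 to 100%: 1.6 for Neo 2329 and 1.7 for MAXN (accuracy tables in the two instructions for use).
- Expected A_RMS of at most 3% (8.4).
- Assumed, because the documents do not give them: the number of affected infants, a between-site gap d of 5 to 10 points in all their pairs, and a neonatal base of 2.5% as a higher alternative.

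**Formula**, with k affected pairs whose difference is d:

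A_RMS = sqrt{[(80 − k) × base² + k × d²] / 80}

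Base 1.6, one infant (k = 3), d = 10: (77 × 2.56 + 3 × 100)/80 = (197.12 + 300)/80 = 6.214; square root 2.49.

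Base 1.7, two infants (k = 6), d = 10: (74 × 2.89 + 6 × 100)/80 = (213.86 + 600)/80 = 10.173; square root 3.19.

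| Base A_RMS | Infants (pairs) | d = 5 | d = 8 | d = 10 |
|---|---|---|---|---|
| 1.6 to 1.7 (adult data) | 1 (3) | 1.84 to 1.93 | 2.21 to 2.28 | 2.49 to 2.56 |
| 1.6 to 1.7 (adult data) | 2 (6) | 2.06 to 2.13 | 2.68 to 2.73 | 3.14 to 3.19 |
| 2.5 (assumed) | 1 (3) | 2.64 | 2.90 | 3.125 |
| 2.5 (assumed) | 2 (6) | 2.77 | 3.25 | 3.64 |

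**Gap needed to reach 3%**: d = sqrt{[80 × 9 − (80 − k) × base²] / k}.

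- Base 1.6 to 1.7: one infant, sqrt(522.88/3) = 13.2 down to sqrt(497.47/3) = 12.9 points; two infants, sqrt(530.56/6) = 9.4 down to sqrt(506.14/6) = 9.2 points.
- Base 2.5: one infant, sqrt(238.75/3) = 8.9 points; two infants, sqrt(257.5/6) = 6.6 points.

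If the gap is added to ordinary sensor error instead of replacing it (A_RMS² = base² + (k/80) × d²), the adult-base results at 10 points are 2.51 to 2.58 for one infant and 3.17 to 3.22 for two, so the choice of model matters little.

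**Mean bias** moves by k × d/80: 3 × 5/80 = 0.19 points for one infant at 5 points, and 6 × 10/80 = 0.75 for two at 10.

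**The case against.** The strongest case on the other side is that the documents give a reason to treat lines differently. Sensors are placed according to the instructions for use. The Masimo instructions say to avoid a limb with an arterial catheter, and the MAXN instructions give priority to a limb free of one. A limb line therefore steers the sensor away from the sampled limb; a puncture does not, and sensor and sample may then share a limb. This stands. A reader might infer that line and puncture carry the same risk of mismatch, and the documents do not support that. They support only that a puncture can produce a mismatch and that the rule does not cover it.

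Second, the exposure is a chain: a significant PDA, no current or planned line, a routine gas still likely, saturation that differs between sites, and an artery and sensor at sites that differ. No link has a stated frequency, and giving all of an infant's pairs the full gap is an upper case. This also stands, and it limits the claim to a possible mismatch. Nor is every such infant certain to be analysed, since an investigator may exclude the infant or note an anomaly. But neither step is required for PDA, and a named PDA rule that specifies a line may suggest that PDA without one is acceptable.

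Third, the puncture remark in 2.1 is general background, and the matching sentence in the synopsis speaks of arterial access. Neither describes how study samples are drawn. The gap rests instead on 5.1 and 4.1, which set no condition on route.

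Fourth, the artery for a future routine puncture may not be known at screening, so new eligibility wording alone would not be enough. That is right, and the fix allows for it.

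**Conclusion.** The point holds as a gap in the named criterion: the rule protects the validity of the reference only for infants with a line, while the study accepts samples taken without one. It should be corrected, because the change is cheap and the affected pairs could not otherwise be identified.

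The size is uncertain and may be small. At the documents' adult A_RMS, one infant does not bring the pooled result to 3% even at a 10-point gap; two infants, 2 of the minimum 27 subjects (7%), do so only at a little over 9 points. A higher neonatal base would lower these gaps, but the documents give no neonatal figure.

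A reader might go further and infer that every infant with a PDA sampled by puncture gives an invalid reference, or that one such infant would fail the sensor. Neither is supported: the first needs a saturation difference and differing sites, and Section 8.4 states 3% as an expectation without a formal pass or fail test.

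**What to change.** 1. In 5.2 and 1.1, and on the screening form, replace the condition about a current or planned line with: *where the arterial sampling for this study, by line or by puncture, relative to the sensor site,* and let it run on into the existing clause on validity. Infants with a PDA whose sampling gives a valid reference stay eligible.
2. In 6.2.1, record the sampled artery and the route on the CRF, beside the sensor location already taken under 6.2.2. Carry PDA status over from screening so that the pairs can be identified; it is not among the items listed in 6.2.7.
3. In 8.4, add a sensitivity analysis of A_RMS, bias and limits of agreement without pairs from infants with a significant PDA whose artery and sensor sites do not match. The sponsor should define matching sites before the data are analysed.

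Cost: one phrase in two sections and the screening form, one CRF field for artery and route plus the PDA status carried over, one extra analysis, and a few more infants screened out. The 80 pairs and 27 subjects do not change.
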